13. APPENDICES

13.1. Appendix 1: Contraceptive Requirements

The allowed methods of contraception described in the following sections are only effective when used consistently, correctly, and in accordance with the product label. The investigator is responsible for ensuring subjects understand how to properly use these methods of contraception.

13.1.1. Female Subjects

Female subjects of childbearing potential must not become pregnant and must use medically accepted methods of contraception with a failure rate of <1% per year throughout the duration of the study and for up to 30 days after last dose of protocol defined study medication.

A female subject is considered of childbearing potential if she has functional ovaries, ducts, and uterus with no impairment that would cause sterility. This includes women with oligomenorrhea (even severe), and women who are peri-menopausal or who have just begun to menstruate.

A female is considered of non-childbearing potential if she is status-post hysterectomy, status-post surgical removal of both ovaries, has current, documented tubal ligation, or is postmenopausal and >2 years without menses. Female subjects who are post-menopausal <2 years must be confirmed menopausal by Follicle Stimulating Hormone (FSH) and estradiol levels.

For sites in Italy: If of reproductive potential, agree to plan and document (or have their partner plan) a birth control strategy (or method) with his/her physician in order to avoid pregnancy throughout the duration of the study and for up to 30 days after last dose of protocol defined study medication.

Contraceptive Methods with a Failure Rate of < 1% per year

- Oral contraceptive, either combined or progestogen alone
- Injectable progestogen
- Implants of etonogestrel or levonorgestrel
- Estrogenic vaginal ring
- Percutaneous contraceptive patches
- Intrauterine device (IUD) or intrauterine system (IUS) that meets the <1% failure per year rate as stated in the product label
- Male partner sterilization (vasectomy with documentation of azoospermia) prior to the female subject's entry into the study, and this male is the sole partner for that subject. For this definition, “documented” refers to the outcome of the investigator's/designee’s medical examination of the subject or

review of the subject's medical history for study eligibility, as obtained via a verbal interview with the subject or from the subject's medical records.

- Double barrier method: condom and occlusive cap (diaphragm or cervical/vault caps) plus spermicidal agent (foam/gel/film/cream/suppository)

13.1.2. Male Subjects

To prevent pregnancy in a female partner, male subjects must use one of the following contraceptive methods:

- Condom and occlusive cap (diaphragm or cervical/vault caps) plus spermicidal agent.
- Male sterilization (e.g., vasectomy with documentation of azoospermia) prior to the subject's entry into the study. For this definition, "documented" refers to the outcome of the investigator's/designee's medical examination of the subject or review of the subject's medical history for study eligibility, as obtained via a verbal interview with the subject or from the subject's medical records.

13.2. Appendix 2: Liver Chemistry Stopping and Follow-up Criteria

1. LIST OF ABBREVIATIONS

ACEi	Angiotensin-converting Enzyme Inhibitors
ADaM	Analysis Data Model
AE	Adverse Event
ALT	Alanine Aminotransferase
APOINT	Peak Mitral Inflow Velocity A
ARB	Angiotensin II Receptor Blockers
AST	Aspartate Aminotransferase
ATC	Anatomical Therapeutic Chemical
BLQ	Below the Limit of Quantification
BMI	Body Mass Index
BP	Blood Pressure
BUN	Blood Urea Nitrogen
CKD-EPI	Chronic Kidney Disease Epidemiology Collaboration
CRF	Case Report Form
CS	Clinically Significant
CTMS	Clinical Trial Management System
DSMB	Data Safety Monitoring Board
EARATIO	Mitral Valve E/A Ratio
ECG	Electrocardiogram
ECHO	Echocardiography
eGFR	Estimated Glomerular Filtration Rate
ENR	All Enrolled Population
EOS	End of Study
EPOINT	Peak Mitral Inflow Velocity E
ERT	Enzyme Replacement Therapy
FS	Fractional Shortening
GGT	Gamma – Glutamyltransferase
GH	General Health
HDL	High Density Lipoprotein
HR	Heart Rate
IA	Interim Analysis
IP	Investigational Product
ITT	Intent-to-Treat
IVSTD	Intraventricular Septum Thickness Diastolic
LDH	Lactate Dehydrogenase
LDL	Low Density Lipoprotein
LVEF	Left Ventricular Ejection Fraction
LVIDd	Left Ventricular Internal Dimension at End Diastole
LVIDs	Left Ventricular Internal Dimension at End Systole
LVMi	Left Ventricular Mass Index
LVPWTD	Left Ventricular Posterior Wall Thickness Diastole

Document: \\quintiles.net\enterprise\Sites\CAMTL\IntProjects\SasData\Amicus\AT1001\AXA23225A\Biostatistics\Documentation\SAP\DR\Amicus_AT1001-042_SAP_Final_v1.0_20190821.docx

Author: Amicus

Version Number: Final v1.0

Version Date: 21AUG2019

Template No.: CS_TP_BS016 Revision 5

Reference: CS_WI_BS005

Effective Date: 01Apr2018

MDRD	Modification of Diet in Renal Disease
MedDRA	Medical Dictionary for Regulatory Activities
MH	Medical History
MWFS	Midwall Fractional Shortening
NCS	Not clinically Significant
PCS	Potentially Clinically Significant
PD	Pharmacodynamic
PF	Physical Functioning
PK	Pharmacokinetic
PSRAE	Possible Suicidality Related Adverse Event
PT	Preferred Term
Q4D	Every Fourth Day
QOD	Every Other Day
RBC	Red Blood Cell
RE	Role Emotional
RI	Renin Inhibitors
RP	Role Physical
SAE	Serious Adverse Event
SAP	Statistical Analysis Plan
SD	Standard Deviation
SF	Social Functioning
SF-36	Short Form 36
SOC	System Organ Class
ULQ	Upper Limit of Quantification
VI	Vitality
WBC	White Blood Cell
WHO-DDE	World Health Organization Drug Dictionary Enhanced

Document: \\quintiles.net\enterprise\Sites\CAMTL\IntProjects\SasData\Amicus\AT1001\AXA23225A\Biostatistics\Documentation\SAP\DR\Amicus_AT1001-042_SAP_Final_v1.0_20190821.docx

Author: Amicus

Version Number: Final v1.0

Version Date: 21AUG2019

Template No.: CS_TP_BS016 Revision 5

Reference: CS_WI_BS005

Effective Date: 01Apr2018

2. INTRODUCTION

This statistical analysis plan (SAP) is based on protocol amendment 1.1 with site-specific addendum 1.1.2, dated 22Jan2018, and it describes the rules and conventions to be used in the presentation and analysis of long-term safety, tolerability, pharmacodynamic (PD), and efficacy data for Protocol AT1001-042, and additionally pharmacokinetic (PK) data for addendum 1.1.2. It describes the data to be summarized and analyzed, including specifics of the statistical analyses to be performed.

A Data Safety Monitoring Board (DSMB) has been chartered to evaluate accumulating safety data in this clinical trial and a DSMB SAP final version 1.1 was effective on 25Oct2015.

3. STUDY OBJECTIVES

3.1. PRIMARY OBJECTIVE

To assess the long-term safety of migalastat HCl in the treatment of subjects with Fabry disease who completed treatment in a previous study of migalastat HCl.

3.2. SECONDARY OBJECTIVES

To explore the long-term efficacy/pharmacodynamics of migalastat HCl in subjects with Fabry disease who completed treatment in a previous study of migalastat HCl.

4. STUDY DESIGN

4.1. GENERAL DESCRIPTION

This study is a multi-center, non-comparative, open-label, long-term extension study of migalastat HCl in subjects with Fabry disease who have completed treatment in a previous trial of migalastat HCl given as monotherapy. All subjects who were eligible for enrollment and completed migalastat HCl monotherapy treatment in a previous study, and who in the opinion of the investigator could benefit from remaining on migalastat HCl treatment were given the option to enroll into this trial. An alternative dosing regimen will be established per the addendum 1.1.2 for those

Document: \\quintiles.net\enterprise\Sites\CAMTL\IntProjects\SasData\Amicus\AT1001\AXA23225A\Biostatistics\Documentation\SAP\DR\Amicus_AT1001-042_SAP_Final_v1.0_20190821.docx

Author: Amicus

Version Number: Final v1.0

Version Date: 21AUG2019

Template No.: CS_TP_BS016 Revision 5

Reference: CS_WI_BS005

Effective Date: 01Apr2018

subjects with renal impairment (glomerular filtration rate (eGFR) < 30 mL/min/1.73m²), confirmed during the enrollment of the original protocol and amendment 1 and 1.1. The number of subjects to be enrolled in this study is expected to be up to 100, but is dependent on the number of eligible subjects completing migalastat HCl treatment in previous studies and who consent to enter this open-label extension study. Therefore, no sample size will be calculated.

The study will consist of a Baseline Visit (Visit 1) which will be performed at the time of the final visit of the previous study, followed by clinic visits every 6 months during the study. For the Addendum 1.1.2 subjects with renal impairment, clinical visits are performed approximately every 3 months. The duration of the treatment will vary among subjects and will continue until the date of regulatory approval or marketing authorization and/or commercialization in the participating subject's country, or study termination by the Sponsor, Amicus Therapeutics (Amicus).

Migalastat HCl will be administered 150 mg every other day (QOD) for subjects enrolled under standard protocol [AT1001-042], or 150 mg every 4th day (Q4D) or every 7th day (Q7D) for Addendum 1.1.2 subjects as a starting point and is subjected to change depending on baseline and follow-up PK and PD assessments for the addendum subjects. Within each participating country, subjects will continue to receive treatment with migalastat HCl within the protocol until one of the study conclusion conditions is met as specified in the protocol section 5.1, or until one of the withdrawal criteria is met as specified in standard protocol section 6.4 or Addendum 1.1.2 section 4.4.

4.2. SCHEDULE OF EVENTS

All study visits should be scheduled from the Baseline Visit (Visit 1), and subsequent visits are planned at approximately 6-month intervals for Amendment 1.1. Follow-up visits will be scheduled one month later with similar window allowances (one week prior and 2 weeks following the designated visit) and will be undertaken only if needed based on PK and PD results from the prior visit. As a comparison, study visits will be planned at approximately 3-month intervals for Addendum 1.1.2 and similarly, follow-up visits will follow one month later. The time and events can be found in Table 1, whereas the time and events of Addendum is described in Table 2.

Document: \\quintiles.net\enterprise\Sites\CAMTL\IntProjects\SasData\Amicus\AT1001\AXA23225A\Biostatistics\Documentation\SAP\DR\Amicus_AT1001-042_SAP_Final_v1.0_20190821.docx

Author: Amicus

Version Number: Final v1.0

Version Date: 21AUG2019

Template No.: CS_TP_BS016 Revision 5

Reference: CS_WI_BS005

Effective Date: 01Apr2018

Table 1 Time and Events Table of Amendment 1.1

Study Month #	Baseline (Month 0) ¹	6 Months (±30 days)	12 Months (±30 days)	Repeat 6 & 12 Month visits in the subsequent years	End of Study (Approximately 30 days after last treatment)
Visit Number	V1	V2	V3	V4, V5, etc	
Assessments					
Review Informed Consent	X				
Review Inclusion/Exclusion Criteria	X	X	X		
Physical Examination	X	X	X		X
Concomitant Medications	X	X	X		X
Vital Signs (BP, HR, RR, Temp)	X	X	X		X
Weight	X	X	X		X
Height	X				X
12 Lead ECG	X	X	X		X
Echocardiography ²	X		X		X ³
Chemistry ^{4 5}	X	X	X		X
Hematology ⁵	X	X	X		X
Urinalysis ⁵	X	X	X		X
24-Hour Urine ⁵	X	X	X		X
eGFR calculation ⁵	X	X	X		X
WBC α-Gal A Activity ⁵	X	X	X		X
Pregnancy Test ⁶	X	X	X		X
Plasma Lyso-GB3	X	X	X		X
Adverse Events	X	X	X		X
SF-36 Survey	X	X	X		X
Study Treatment Supply/Resupply/Return ⁷	X	X	X		X
Intermediate Subject Contact ⁸	X	X	X		X

- Assessments collected for the end of study visit in the previous study (which are also required at Baseline for the current study) will serve as Baseline Visit 1 assessments for this study. The visit window for the last treatment visit will apply for the completion of such assessments. Assessments required at Baseline (Visit 1) that are not performed as part of the last treatment visit in the previous study will have a visit window of +30 days.
- ECHOs will be read centrally.

Document: \\quintiles.net\enterprise\Sites\CAMTL\IntProjects\SasData\Amicus\AT1001\AXA23225A\Biostatistics\Documentation\SAP\DR\Amicus_AT1001-042_SAP_Final_v1.0_20190821.docx

Author: Amicus

Version Number: Final v1.0

Version Date: 21AUG2019

Template No.: CS_TP_BS016 Revision 5

Reference: CS_WI_BS005

Effective Date: 01Apr2018

3. ECHO is to be performed for subjects who withdraw from the study and did not have an ECHO performed within the previous 6 months.
4. Subjects must fast for approximately 8 or more hours before serum chemistry is performed.
5. In the event of an abnormal lab result, at the investigator's discretion, the test can be repeated in an unscheduled visit and sent to the central laboratory for analysis.
6. Urine pregnancy test to be performed at Baseline Visit 1 according to previous protocol; thereafter the urine pregnancy test will be performed locally using dipstick.
7. Study Treatment Supply for Study AT1001-042 is intended to occur on Baseline (Visit 1) or in subsequent days within the allowable window for this visit.
8. Subjects will receive a telephone contact, or contact using another acceptable method, approximately midway between visits to assess Adverse Events and dosing compliance. It is better to have the phone contact performed earlier or later than scheduled, rather than not at all.

Document: \\quintiles.net\enterprise\Sites\CAMTL\IntProjects\SasData\Amicus\AT1001\AXA23225A\Biostatistics\Documentation\SAP\DR\Amicus_AT1001-042_SAP_Final_v1.0_20190821.docx

Author: Amicus

Version Number: Final v1.0

Version Date: 21AUG2019

Template No.: CS_TP_BS016 Revision 5

Reference: CS_WI_BS005

Effective Date: 01Apr2018

Table 2 Time and Events of Site Addendum 1.1.2

Study Month (Visit)	Baseline (Month 0) ¹ (V1A)	Months 3 (V2A) 15 (V6A) 27 (V10A)	Months 4, 16, & 28 (Follow- up) ²	Months 6 (V3A) 18 (V7A) 30 (V11A)	Months 7, 19, & 31 (Follow- up) ²	Months 9 (V4A) 21 (V8A) 33 (V12A)	Months 10, 22, & 34 (Follow- up) ²	Months 12 (V5A) 24 (V9A) 36 (V13A)	Months 13, 25, & 37 (Follow- up) ²	End of Study (Approximately 30 days after last treatment)
Visit Window		-7 to +14 days	Phone	-7 to +14 days	Phone	-7 to +14 days	Phone	-7 to +14 days	Phone	
Assessments										
Review Informed Consent	X									
Review Inclusion/Exclusion Criteria	X	X	X	X	X	X	X	X	X	
Physical Examination	X			X				X		X
Concomitant Medications	X	X		X		X		X		X
Vital Signs (BP, HR, RR, Temp)	X	X		X		X		X		X
Weight	X	X		X		X		X		X
Height	X									X
12-Lead ECG	X			X				X		X
Echocardiography ³	X							X		X ⁴
Chemistry ⁵	X	X	X	X	X	X	X	X	X	X
Hematology ⁵	X	X	X	X	X	X	X	X	X	X
Urinalysis ⁵	X	X	X	X	X	X	X	X	X	X
eGFR Calculation ⁵	X	X	X	X	X	X	X	X	X	X
WBC α-Gal A Activity	X			X				X		X

Document: \\quintiles.net\enterprise\Sites\CAMTL\IntProjects\SasData\Amicus\AT1001\AXA23225A\Biostatistics\Documentation\SAP\DR\Amicus_AT1001-042_SAP_Final_v1.0_20190821.docx

Author: Amicus

Version Number: Final v1.0

Version Date: 21AUG2019

Template No.: CS_TP_BS016 Revision 5

Reference: CS_WI_BS005

Effective Date: 01Apr2018

Table 2 Time and Events of Site Addendum 1.1.2 (Continued)

Study Month (Visit)	Baseline (Month 0) ¹ (V1A)	Months 3 (V2A) 15 (V6A) 27 (V10A)	Months 4, 16, & 28 (Follow-up) ²	Months 6 (V3A) 18 (V7A) 30 (V11A)	Months 7, 19, & 31 (Follow-up) ²	Months 9 (V4A) 21 (V8A) 33 (V12A)	Months 10, 22, & 34 (Follow-up) ²	Months 12 (V5A) 24 (V9A) 36 (V13A)	Months 13, 25, & 37 (Follow-up) ²	End of Study (Approximately 30 days after last treatment)
Plasma Lyso-Gb ₃	X	X	X	X	X	X	X	X	X	X
Adverse Events	X	X	X	X	X	X	X	X	X	X
Subject Diary ⁶		X	X	X	X	X	X	X	X	
Study Treatment Supply/Resupply/Return ⁷	X	X		X		X		X	X	X
Urine Collections for Migalastat Assessments ⁸	X	(X) ⁹	(X) ⁹	(X) ⁹	(X) ⁹	(X) ⁹	(X) ⁹	(X) ⁹	(X) ⁹	
Blood Sampling for PK Assessments ¹⁰	X	X	X	X	X	X	X	X	X	

α-Gal A = α-galactosidase A; BP = blood pressure; ECG = electrocardiogram; eGFR = estimated glomerular filtration rate; Lyso-Gb₃ = globotriaosylsphingosine; HR = heart rate; PK = pharmacokinetics; RR = respiratory rate; Temp = temperature; WBC = white blood cell.

NOTE: Following Month 12 (or 13, if needed), visits will repeat for the duration of the study, occurring every 3 mos with follow-up visits one month later, if needed.

1. All Baseline safety assessments will be repeated prior to first administration of migalastat at re-entry into the study.
2. Follow-up visits will occur only if needed, based on PK/PD assessments performed at the prior visit. If needed, the subject may be contacted by phone and have assessments done at the study site or drawn by a home healthcare professional. All samples will be sent to the central Laboratory.
3. Echocardiograms will be read centrally.
4. Echocardiogram is to be performed upon withdrawal from the study only if one was not performed within the previous 6 months.
5. In the event of an abnormal lab result, at the investigator's discretion, the test can be repeated in an unscheduled visit and sent to the central laboratory for analysis.
6. A diary will be maintained throughout the study to record study drug administration and the occurrence of any adverse events.
7. Study Treatment Supply for Study AT1001-042 is intended to occur on Baseline (Visit 1) or on subsequent days within the allowable window visits.
8. See [Appendix 1](#) for urine collection intervals.
9. Additional urine collections for migalastat assessment will be done prior to any change in dose regimen.

Document: \\quintiles.net\enterprise\Sites\CAMTL\IntProjects\SasData\Amicus\AT1001\AXA23225A\Biostatistics\Documentation\SAP\DR\Amicus_AT1001-042_SAP_Final_v1.0_20190821.docx

Author: Amicus

Version Number: Final v1.0

Version Date: 21AUG2019

Template No.: CS_TP_BS016 Revision 5

Reference: CS_WI_BS005

Effective Date: 01Apr2018

10. See [Appendix 1](#) for PK assessment times.

Document: \\quintiles.net\enterprise\Sites\CAMTL\IntProjects\SasData\Amicus\AT1001\AXA23225A\Biostatistics\Documentation\SAP\DR\Amicus_AT1001-042_SAP_Final_v1.0_20190821.docx

Author: Amicus

Version Number: Final v1.0

Version Date: 21AUG2019

Template No.: CS_TP_BS016 Revision 5

Reference: CS_WI_BS005

Effective Date: 01Apr2018

5. PLANNED ANALYSES

The following analyses will be performed for this study:

- Analyses for DSMB (described elsewhere in the DSMB Charter)
- Final Analysis

5.1. DATA SAFETY MONITORING BOARD (DSMB)

A DSMB SAP describing the methodology and presentation of results and access to results is provided by IQVIA as a separate document. The final version (Final V1.1) of DSMB SAP was effective on 25Oct2015.

5.2. INTERIM ANALYSIS

There will be no interim analysis (IA) for this study.

5.3. FINAL ANALYSIS

All final, planned analyses identified in this SAP will be performed by IQVIA Biostatistics following Sponsor Authorization of this Statistical Analysis Plan and Database Lock.

6. ANALYSIS SETS

6.1. ALL ENROLLED (ENR)

The all subjects enrolled (ENR) set will contain all subjects who provide informed consent for this study.

6.2. INTENT-TO-TREAT [ITT]

The Intent-to-Treat (ITT) Population will include subjects who take at least one dose of Investigational Product (IP) after they have enrolled into this open-label extension study (excluding addendum 1.1.2 subject), and is the primary population of interest. All safety, efficacy and demography summaries will be based on the ITT population. Protocol

Document: \\quintiles.net\enterprise\Sites\CAMTL\IntProjects\SasData\Amicus\AT1001\AXA23225A\Biostatistics\Documentation\SAP\DR\Amicus_AT1001-042_SAP_Final_v1.0_20190821.docx

Author: Amicus

Version Number: Final v1.0

Version Date: 21AUG2019

Template No.: CS_TP_BS016 Revision 5

Reference: CS_WI_BS005

Effective Date: 01Apr2018

deviations will be reported in a listing.

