8.2. Safety

8.2.1. Safety Assessments

Safety assessments include the following:

- Adverse events (AEs), possible suicidality related adverse events (PSRAEs), and serious adverse events (SAEs)
- Withdrawal due to AEs
- Vital signs (blood pressure, body temperature, respiration rate, and heart rate) and weight
- Hematology, chemistry, and urinalysis parameters
- Echocardiography (ECHO)
- Electrocardiograms (ECGs)
- Stopping criteria

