8.2.2. Stopping Criteria

Subjects must discontinue study medication and be withdrawn from the study if they meet any of the following stopping criteria:

- 30% increase in serum creatinine from Baseline (Visit 1) confirmed by repeat analysis in fully hydrated subject
- 25% decrease from Baseline in cardiac ejection fraction as determined by echocardiogram
- Cerebrovascular event with significant sequelae, including stroke
- An eGFR value of $< 30 \text{ mL/min/1.73m}^2$

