10.3.1. Analysis Populations

The Intent-to-Treat (ITT) Population is the primary population of interest and will include subjects who take at least one dose of IP after they have enrolled into this open-label extension study.

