10.3.2. Analysis Data Sets

All safety and demography summaries will be based on the ITT population.

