10.3.4.2. Efficacy Analyses

Since no hypothesis testing is planned for this study, all efficacy parameters will be summarized using descriptive statistics for subjects in the ITT population. Summaries of the efficacy variables will be provided for the value at baseline and at each post-baseline time point and the change from baseline at each post-baseline time point.

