17. EFFICACY OUTCOMES

17.1. EFFICACY OUTCOMES AND VARIABLES

All efficacy outcomes will include all subjects (excluding the renal impairment subject) and will be summarized using nominal visits (not including unscheduled visit or early termination) and descriptive statistics. Efficacy assessments will be performed at the Baseline Visit, followed by subsequent clinic visits in every 6 months until the

Document: \\quintiles.net\enterprise\Sites\CAMTL\IntProjects\SasData\Amicus\AT1001\AXA23225A\Biostatistics\Documentation\SAP\DR\Amicus_AT1001-042_SAP_Final_v1.0_20190821.docx

Author: **Amicus** Version Number: **Final v1.0**
 Version Date: **21AUG2019**

Template No.: CS_TP_BS016 Revision 5 Reference: CS_WI_BS005

Effective Date: 01Apr2018

End of Study visit. All efficacy outcomes will follow the same visit pattern unless otherwise specified. Descriptive statistics will be calculated for baseline and each post-baseline visit (as well as time point if applicable), followed by change from baseline at that visit. Baseline is defined in section 7.2, whereas change from baseline is defined in section 7.6.

The efficacy endpoints to be presented are

- eGFR_{MDRD} and eGFR_{CKD-EPI}
- Plasma lyso-Gb₃ (Plasma globotriaosylsphingosine)
- Measurement of white blood cell (WBC) α-Gal A activity
- Measurement of 24-hour urine protein
- Measurement of left ventricular mass (LVM) and LVM index (LVMi), as assessed by echocardiography
- Measurement in ejection fraction, as assessed by echocardiography
- Measurement of fractional shortening, as assessed by echocardiography
- Measurement of left ventricular internal dimension (LVIDd and LVIDs), midwall fractional shortening (MWFS), and wall thicknesses, as assessed by echocardiography
- Measurement of patient reported Quality of Life as assessed by the Short Form 36 (SF-36)

Each endpoint (consisting of one or more variables) will be summarized in a table. Listings will be provided by domain or sub-domain categories, e.g. Laboratory categories - Chemistry, Hematology, Urinalysis, Echocardiography, and Questionnaire.

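### The SAP's ITT set excludes the addendum 1.1.2 subject as a person, although protocol 10.3.1 keeps everyone dosed; the exclusion should be by study period

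*SAP*

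**What the plan says.** Protocol 10.3.1 makes ITT the primary population. It "will include subjects who take at least one dose of IP after they have enrolled into this open-label extension study", with no exception. Protocol 10.3.2 adds: "All safety and demography summaries will be based on the ITT population". Under Protocol 10.3.4.2, "all efficacy parameters will be summarized using descriptive statistics for subjects in the ITT population".

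SAP 6.2 keeps the dosing rule but confines the set to subjects "who take at least one dose of Investigational Product (IP) after they have enrolled into this open-label extension study (excluding addendum 1.1.2 subject". It uses that set for safety, efficacy and demography. SAP 17.1 states: "All efficacy outcomes will include all subjects (excluding the renal impairment subject". SAP 12, 15, 16 and 18 tie demography, exposure, compliance and safety outputs to ITT, so the exclusion reaches all of them.

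SAP 2 gives the basis of the plan: "This statistical analysis plan (SAP) is based on protocol amendment 1.1 with site-specific addendum 1.1.2". The SAP's table of contents lists a section 6.3 headed with the addendum's number. Neither the text of 6.3 nor the addendum was available for this review.

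**The concern.** Both exclusions name a person, not a stretch of follow-up. A subject who took a dose after enrolling under the main protocol met the 10.3.1 definition at that moment, and later entry into an addendum does not undo it.

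The route into the addendum matters. SAP 4.1 describes it as being for subjects with an eGFR below 30. Protocol 8.2.2 says: "Subjects must discontinue study medication and be withdrawn from the study if they meet any of the following stopping criteria", and an eGFR below 30 is one of those criteria. Protocol 8.2.1 lists "Stopping criteria" among the safety assessments. eGFR is also an efficacy endpoint, summarized by visit and as an annualized slope. Membership of the primary set would then depend on an outcome seen after entry, which an ITT definition is meant to prevent.

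At stake are the subject's main-protocol contributions to the ITT tables, and the count of subjects in the ITT disposition table who left on a stopping criterion.

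**Working it through.** The plan has no sample size, power or alpha to reproduce. The check is a comparison of texts, followed by an illustration of size.

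**1. The two definitions**

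| | Dosing rule | Exclusion | Used for |
|---|---|---|---|
| Protocol 10.3.1, 10.3.2, 10.3.4.2 | at least one dose after enrolment | none | safety, demography, efficacy |
| SAP 6.2, 17.1, 18 | same | addendum 1.1.2 / renal impairment subject | safety, demography, efficacy |

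They differ only in the exclusion, and the exclusion is by subject.

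**2. Was the subject dosed earlier under the main protocol?** No sentence says so. The following point that way:
- SAP Table 2, footnote 1, speaks of re-entry, with baseline safety assessments repeated.
- SAP Appendix 1 describes addendum subjects as re-enrolled.
- SAP 4.1 says the impairment was confirmed under the original protocol and amendments 1 and 1.1, although its phrasing is ambiguous.
- Protocol 6.3, criterion 1, bars entry if the last eGFR in the previous study was below 30, unless a recent measured GFR was above 30. Most entrants therefore started above the limit.
- Protocol 8.2.2 requires withdrawal once eGFR is below 30.

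Together these make earlier main-protocol dosing probable. The length of that follow-up is not given.

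**3. How many subjects?** SAP 6.2, SAP 17.1 and two schedule headings in Appendix 1 use the singular. SAP 4.1, SAP 15 and the visit paragraph of Appendix 1 use the plural. Since the addendum is site-specific, one subject is the better-supported reading.

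**4. Effect on the mean eGFR slope.** Let N be the full set, m the number excluded, and d the gap between the excluded subject's slope and the mean of the others. Then full-set mean minus reduced-set mean = m × d / N. The documents give no slopes, so d = 3 to 15 mL/min/1.73m² per year in absolute size is an assumption. N = 100 is the ceiling in Protocol 6.1. SAP 8.5 has six sex-by-proteinuria cells, so an average cell is 100/6, about 17. N = 50 and a cell of 5 are assumed.

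| m = 1 | d = 3 | d = 15 |
|---|---|---|
| N = 100 | 3/100 = 0.03 | 15/100 = 0.15 |
| N = 50 | 3/50 = 0.06 | 15/50 = 0.30 |
| cell of 17 | 3/17 = 0.18 | 15/17 = 0.88 |
| cell of 5 | 3/5 = 0.60 | 15/5 = 3.00 |

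Two subjects would double each figure. The sign follows the sign of d, which is unknown.

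**5. Effect on counts, if the subject left on the eGFR criterion.** The stopping-criteria row in the ITT disposition table would go from 1/100 to 0/99, or from 3/100 = 3.0% to 2/99 = 2.0%.

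**6. Would one flag be enough to split the periods?** No.
- SAP 15 computes exposure from first to last dose and ignores interruptions. An uncut last dose date would count any gap before re-entry as exposure.
- SAP 16 expects one dose every two days: 365/2 = 182.5 doses in 365 days. The addendum intervals in SAP 15 imply 365/4 = 91.25 or 365/7 = 52.1.
- SAP 17.1.1 fits the slope over all available visits to end of study, which would run into addendum visits unless cut.

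**The case against.** The strongest reply is that the comparison is incomplete. The SAP rests on the addendum as well as on amendment 1.1, and SAP 4.1 cites the addendum's own section 4.4, so the addendum may have changed the analysis populations. SAP 6.3 may define a separate set. A reader might infer that the sponsor gave no reason and no rule for the subject's main-protocol data. The documents do not support that, because the place where such a rule would stand could not be read. This part of the reply stands in full.

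Separate handling also has a visible basis: a different dosing interval, 3-month visits, a new baseline, separate visit labels, and an addendum schedule with no row for SF-36 or for the main schedule's 24-hour urine test. This justifies separating the addendum period. It does not justify removing the time before it.

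A reader might also infer that safety data disappear. They do not. The enrolled set in SAP 6.1 holds everyone who consents, SAP 10 accounts for all of them and shows disposition for the addendum population, SAP 18.1 lists all adverse events, and Appendix 1 lists all data by default. The loss is confined to the ITT summaries.

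Finally, the harm is conditional on earlier main-protocol dosing, and the slope figures rest on assumed gaps in a study with no hypothesis tests. That also stands. What remains is the difference in wording. A separate addendum set in 6.3 would not by itself return main-protocol data to the ITT tables. Only text that overrides 6.2, or an addendum that changes 10.3.1, would do so.

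**Conclusion.** The concern holds in a limited form and should be fixed. Measured against the base protocol, the set that the SAP calls ITT is not the protocol's ITT, because SAP 6.2 and 17.1 exclude by person and SAP 18 carries this into the primary, safety objective. If the subject was dosed under the main protocol, which is probable but inferred, data leave the primary set because of a later eGFR below 30.

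The effect on overall means is small: 0.03 to 0.15 mL/min/1.73m² per year for one subject in 100, under the assumed gap. Small subgroup cells are more exposed. It is tempting to read the exclusion as flattering the renal results. The documents give no slope for this subject or for the others, so the direction cannot be stated. Confidence is medium, because SAP 6.3 and the addendum may already settle the matter.

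**What to change.** In SAP 6.2 and 17.1, replace the exclusion by subject with one by period. Keep every dosed subject in ITT with data up to the end of main-protocol treatment, and present addendum-period data separately. Apply one cut-off throughout:

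- the last dose date, for exposure (SAP 15) and compliance (SAP 16);
- the last visit used in the eGFR slopes (SAP 17.1.1 and 17.1.2);
- the reason for leaving main-protocol treatment, in disposition (SAP 10);
- adverse events, by onset date, with a rule for events ongoing at re-entry.

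Use one term for the subject in place of two, state how many are affected, and align the wording with SAP 6.3. If 6.3 or the addendum already places the main-protocol data, a cross-reference in 6.2 and 17.1 may be enough. If the reduced set is kept, give it a name other than ITT and document the departure from Protocol 10.3.1.

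The cost is SAP wording, a few derivation rules and some footnotes. Addendum visits already carry their own labels in Appendix 1, which makes the split practical. The renal summaries may become slightly less favourable, though this is not certain.
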